### **End of the study**

A patient may exit from the study for any of the following reasons: 1. Death. 2. In any case, when the 36 weeks' postconceptional age is reached. 3. If parents or guardians withdraw an already given consent for the participation (in that case the patient will keep receiving the whole routine clinical assistance data acquired up to that point will be immediately destroyed)

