### **Inclusion criteria:**

- i. GA between 240/7 and 286/7 weeks
- ii. Diagnosis of RDS. The diagnosis of RDS will be based on clinical manifestations (tachypnea, nasal flaring and or grunting) and a fraction of inspired oxygen (FiO2) greater than 0.25 for target saturation of peripheral oxygen (SpO2) 89%–94%
- iii. Age <2 hours
- iv. Informed parental consent has been obtained

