### **Secondary outcomes**

- (1) Airleaks (pneumothorax and/or pneumomediastinum) occurred during treatment of RDS.
- (2) BPD, defined according to the NICHD definition.

- (3) Haemodynamically significant PDA, defined according to local NICU protocols.
- (4) Retinopathy of prematurity (ROP) >2nd stage.
- (5) Necrotising enterocolitis (NEC)  $\geq$ 2nd stage.
- (6) Intracranial haemorrhage (IVH)  $\geq$ 3rd grade.
- (7) In-hospital mortality.
- (8) Composite mortality/BPD
- (9) Weekly weight gain (in grams/day) for the first 4 weeks of life or until NICU discharge, whichever comes first
- (10) Duration of non-invasive respiratory assistance.
- (11) Duration of hospitalisation.
- (12) Rate of surfactant treatment.
- (13) Rate of thick secretions causing an airway obstruction.
- (14) Rate of nasal trauma

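### Exit from the study at 36 weeks' postconceptional age conflicts with in-hospital mortality and duration of hospitalisation, and the plan never says when outcome data collection ends

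*Combined protocol and SAP*

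**What the plan says.** The End of the study section opens with "A patient may exit from the study for any of the following reasons" and gives three reasons: death, withdrawal of consent and, as the second item, "In any case, when the 36 weeks' postconceptional age is reached". It says what happens to collected data only for withdrawn consent, where they are destroyed.

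The Secondary outcomes section includes "In-hospital mortality" as item (7) and "11) Duration of hospitalisation". Neither has a time limit. Items (4), ROP above stage 2, (8), "8) Composite mortality/BPD", and (10), duration of non-invasive respiratory assistance, give no end of observation or assessment age. By contrast, item (9), weight gain, does have an explicit window: four weeks of life or NICU discharge, whichever is earlier.

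The Data collection section says that all trial data are routine items from the clinical notes, entered daily on web forms. Its follow-up list repeats (4), (7), (8) and (11), with neither a 36-week limit nor a statement that entry continues after exit. The Statistical methods section plans a t test or Mann-Whitney test for continuous outcomes. It has no rule for an infant who is still in hospital, or still on support, at exit.

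**The concern.** An in-hospital death and a length of stay are complete only at discharge or death. A rule that takes every infant out of the study at a fixed postconceptional age closes observation earlier for anyone still admitted. Three things are then at stake:

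- Deaths in hospital after 36 weeks go uncounted, and those infants appear as survivors in (7) and, unless its mortality part is meant to stop at 36 weeks, in (8).
- If the exit date stands in for the end of stay, the recorded stay of an infant still admitted reflects gestational age at birth. Treatment shows only in the fact of still being in hospital. A true difference between arms would shrink.
- With 20 units entering data, some may close the record at 36 weeks and others at discharge, so one variable would carry two definitions.

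**Working it through.** **Reading the sections together.** The word *may* introduces all three exit reasons, including death, where exit is not optional. It can therefore mean only that these are the ways an infant can leave. The 36-week item adds the emphatic *in any case*. Against that, outcomes (7) and (11) end at discharge or death by their names, and the follow-up list repeats both. Nothing links the two.

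**Length of the observation window.** Inputs: exit at 36+0 weeks (End of the study); birth at 24+0 to 28+6 weeks (Inclusion criteria). Formula: last observable day of life = 36 × 7 − gestational age at birth in days = 252 − gestational age.

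| Born at | Age in days | Last day observed |
|---|---|---|
| 24+0 | 168 | 84 |
| 25+0 | 175 | 77 |
| 26+0 | 182 | 70 |
| 27+0 | 189 | 63 |
| 28+0 | 196 | 56 |
| 28+6 | 202 | 50 |

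The cap differs by 84 − 50 = 34 days across the eligible range. Two infants still in hospital at 36 weeks, born at 24+0 and 28+6, would be recorded as staying 84 and 50 days whenever they actually went home.

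**Which outcomes are touched.**

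- (7) and (11): direct conflict by name.
- (8): inherits a mortality window that is not stated.
- (10): no end stated; capped for infants still supported at 36 weeks.
- (4): no assessment age stated; findings after 36 weeks would be missed if there are any.
- (9): unaffected, since four weeks of life ends at 28+0 to 32+6 weeks.
- Primary outcome: unaffected, since it closes 72 hours after birth. The planned 170 per group rests on it and does not change.

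**How much a cap could shrink a difference in stay (illustration only).** The documents give no discharge ages. Assume that postconceptional age at discharge is normal with mean m and SD 14 days, that the true benefit is 5 days, and that everyone is capped at c = 252 days. The mean loss from capping, relative to c, uses

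g(m) = (c − m)Φ((c − m)/14) + 14φ((c − m)/14),

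where the capped mean is c − g(m). The observed difference is g(m − 5) − g(m).

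| Mean discharge | Controls cut off | g(m − 5) − g(m) | Observed difference |
|---|---|---|---|
| 34 weeks | 16% | 19.56 − 15.17 | 4.4 days |
| 35 weeks | 31% | 13.52 − 9.77 | 3.8 days |
| 36 weeks | 50% | 8.44 − 5.59 | 2.9 days |
| 37 weeks | 69% | 4.64 − 2.77 | 1.9 days |
| 38 weeks | 84% | 2.20 − 1.17 | 1.0 day |

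The loss is small if most infants leave before 36 weeks and large if most leave after. The table concerns length of stay only. It says nothing about mortality, ROP or the composite.

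**The case against.** The strongest reply is that truncation is not established. The exit section never says that data collection stops at 36 weeks. The follow-up list contains in-hospital mortality and duration of hospitalisation with no such limit, and the source is the hospital record, which exists until discharge. The sponsor may well intend collection to discharge. This stands: a reader might infer that these outcomes are certain to be cut off, but the documents support only that they would be if the rule is followed as written. It does not remove the need for a change. If collection to discharge is intended, the exit section misstates it.

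Three further limits also stand. First, a reader might infer that ROP and the composite run past 36 weeks just as (7) and (11) do. The documents give no assessment age for ROP and no mortality window for the composite, so all that can be said is that their windows are missing. A composite defined at 36 weeks would be coherent. Second, a reader might infer that the secondary outcomes are generally driven by gestational age. That holds only for durations, only for infants still admitted or supported at 36 weeks, and only if the exit date is used as the end. No section prescribes that use. Third, the attenuation table is built on assumed discharge ages, an assumed spread and an assumed effect, and is not evidence from this trial.

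**Conclusion.** The concern holds as an unresolved contradiction. The exit rule closes observation on day 50 to day 84 of life, depending on gestational age at birth, while (7) and (11) need observation to discharge or death. Outcomes (4), (8) and (10) have no stated end and would be cut at the same point. The window follows from the documents' own figures. The share of infants still in hospital at 36 weeks is not given, so the number of missed deaths and the loss in any difference in stay cannot be sized. Under the assumptions shown, a true 5-day difference would appear as anything from 4.4 days down to 1.0 day.

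Because the cap depends on a baseline factor, the likely harm is mainly dilution. Bias between arms in recorded stay would also arise if gestational age were unbalanced, which simple randomisation does not rule out. The matter is worth correcting before data lock, but it does not threaten the primary result.

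**What to change.** In the End of the study section, separate the 36-week time point from the end of outcome data collection. State that (7) and (11) are collected from the clinical notes until first discharge home or death. Say the same for (4), (10) and the mortality part of (8), unless the sponsor defines these at 36 weeks, in which case write that age into the outcome. Carry the same end dates into the Data collection section so that all units close records alike.

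If collection must stop at 36 weeks, rename the outcomes accordingly: death by 36 weeks, death by 36 weeks or BPD, ROP above stage 2 by 36 weeks, and duration of non-invasive support up to 36 weeks. Then drop duration of hospitalisation.

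The change concerns data collection only and alters no treatment rule. The data are already routine chart items, so no visit or procedure is added. The cost is a few sentences of text, a later close of the case report form and a somewhat later database lock.

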### **Randomization**

Neonates will be randomised and assigned either to NCPAP or NHFOV arms with a 1:1 ratio, when patients fulfil all inclusion criteria. Simple randomisation will be done according to a computer-generated random number table and will be posted in a

specific secured website available on 24/7. Twins will all be allocated in the same treatment group. Infants randomised to one arm cannot crossover to the other or vice-versa during the study.

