### **Blinding**

Operators and care providers will not be blinded, and the outcome assessors and data analysts will be blinded to the intervention

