### **Primary outcomes**

The primary outcomes will be the respiratory support failure determined by the need for IMV within 72 hours from birth. The respiratory support failure will be considered if one of the following occurs: (1) severe respiratory acidosis (defined as  $\text{PaCO}_2 > 60 \text{ mm Hg}$  with  $\text{pH} < 7.2$ ) for at least 1 hour; (2) hypoxia refractory to study intervention (defined as  $\text{SpO}_2 < 90\%$ , with  $\text{FiO}_2 = 0.4$  and maximal pressures allowed in the study arm) for at least 1 hour after the administration of surfactant; (3) severe apnoea (defined as recurrent apnoea with  $> 3$  episodes/hour associated with heart rate  $< 100/\text{min}$  or a single episode of apnoea requiring bag and mask ventilation) and (4) attending physician determined that urgent intubation is necessary.

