### **Statistical methods**

Outcomes will be analysed on an intention-to-treat basis. We will calculate a risk difference (with 95%CI) for dichotomous outcomes and mean (with 95%CI) or median (25–75th percentile, using Hodges-Lehmann) differences for continuous outcomes between the study groups. Continuous variables will be compared using

Student's t test or the Mann-Whitney rank sum test as appropriate. Categorical variables were compared using the  $\chi^2$  test. P values  $< 0.05$  were considered statistically significant.

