### **Data monitoring board**

An independent data monitoring committee belonging to the Central Ethics Committee of Children's Hospital of Chongqing Medical University has been established for the trial. This committee will perform interim data analysis, investigate compliance with the trial and monitor adverse events. Formal interim analyses of efficacy will be carried out by the DMB when 25%, 50% and 75% of the outcome data were available. The board will advise the principal investigator who will remain the only responsible for the trial conduction and for any eventual decision to stop or continue it.

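### Destroying collected data when consent is withdrawn contradicts the intention-to-treat analysis; the primary risk difference is materially biased only if withdrawal depends on both arm and outcome

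*Combined protocol and SAP*

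**What the plan says.** Under End of the study, one route out of the trial is "If parents or guardians withdraw an already given consent for the participation". The same sentence states that routine care continues and that "data acquired up to that point will be immediately destroyed". Another route out is reaching 36 weeks' postconceptional age, so consent can be withdrawn up to then.

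Statistical methods states: "Outcomes will be analysed on an intention-to-treat basis". It specifies a risk difference with 95% CI for dichotomous outcomes. It gives no rule for missing or erased infants and no sensitivity analysis.

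The primary outcome is the "need for IMV within 72 hours from birth" (Primary outcomes). Blinding states: "Operators and care providers will not be blinded, and the outcome assessors and data analysts will be blinded to the intervention". It does not say whether parents know the arm.

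The sample size section states no allowance for lost infants. Withdrawal is not among the items listed under Data collection. Allocation is held on a "specific secured website available on 24/7" (Randomization), which is described separately from the web-based case report forms. The protocol does not say whether the allocation record is covered by the erasure rule.

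**The concern.** An infant whose record has been destroyed cannot be analysed as randomised, so the two rules cannot both be followed. This differs from ordinary dropout, where the outcome was never seen. Here the primary outcome is complete at 72 hours, and the rule reaches back to remove a valid, observed result.

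At stake is the primary risk difference. Staff know the arm and the outcome, and the choice to withdraw could come after both. If families of failed infants withdraw more often in one arm than in the other, the retained sample misstates the difference, in either direction. The protocol plans no count of erasures by arm from which a reader could judge this.

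**Working it through.** **1. How long a known outcome remains erasable.** Gestational age at entry runs from 24+0 weeks (168 days) to 28+6 weeks (202 days). The exit at 36 weeks is day 252 if postconceptional age is counted on the same scale as gestational age. That is 252 − 168 = 84 days after birth at the youngest age and 252 − 202 = 50 days at the oldest. Subtracting the 3 days of the primary outcome window leaves 81 and 47 days.

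**2. The plan's own figure.** Sample size calculation gives 30% failure on NCPAP, a target difference of 15 points (so 15% on NHFOV), alpha 0.05, power 90% and 170 per group. I assume a two-sided test.

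- Pooled two-proportion formula: n = [1.96√(2 × 0.225 × 0.775) + 1.2816√(0.3 × 0.7 + 0.15 × 0.85)]² / 0.15² = 160.8, so 161 per group. With continuity correction it is 174, within 3% of the stated 170. (161/0.95 also rounds up to 170, but no 5% allowance is stated.)
- Power = Φ[(d − 1.96·s0)/s1], where s0 and s1 are the pooled and unpooled standard errors. At 170 per group: (0.15 − 1.96 × 0.0453)/0.0446 = 1.374, giving 91.5%.

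**3. Model for erasure.** Let w be the share of an arm erased, p its true failure rate, and r how many times as likely a failure is to withdraw as a non-failure. Then non-failures withdraw at wn = w/(p·r + 1 − p), failures at wf = r·wn, and the failure rate in the retained infants is p′ = p(1 − wf)/(1 − w).

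With w = 5% and r = 3:
- NCPAP: wn = 0.05/1.6 = 0.03125 and wf = 0.09375, so p′ = 0.3 × 0.90625/0.95 = 0.2862 (about 4.8 failures and 3.7 non-failures erased).
- NHFOV: wn = 0.05/1.3 = 0.03846 and wf = 0.11538, so p′ = 0.15 × 0.88462/0.95 = 0.1397 (about 2.9 failures and 5.6 non-failures erased).

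If all 5% (8.5 infants) are failures:
- NCPAP: (51 − 8.5)/161.5 = 0.2632.
- NHFOV: (25.5 − 8.5)/161.5 = 0.1053.

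**4. Results.** The false-positive column sets both arms at 30% and takes one final two-sided test at 5%, ignoring the interim looks and any clustering of twins. In the one-arm rows, power is for erasure on the NCPAP side. On the NHFOV side the effect is exaggerated instead.

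| Assumed erasure | Difference (points) | Power | False-positive rate |
|---|---|---|---|
| None | 15.0 | 91.5% | 5.0% |
| 5% of each arm, unrelated to outcome | 15.0 | 90.1% | 5.0% |
| 5% of each arm, r = 3 | 14.7 | 89.9% | 5.0% |
| 1% of one arm, r = 3 | 14.7 (NCPAP side) or 15.2 (NHFOV side) | 90.5% | 5.0% |
| 2% of one arm, r = 3 | 14.5 or 15.4 | about 89% | 5.1% |
| 5% of one arm, r = 3 | 13.6 or 16.0 | 85.5% | 5.9% |
| 5% of one arm, failures only (extreme) | 11.3 or 19.5 | 72% | 11.5% |

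**5. What a count by arm makes possible.** Knowing only how many infants were erased per arm, one can bound the difference on all 170 randomised per arm by assigning the erased infants all failures or none.

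- Five erased per arm, 50/165 vs 25/165 retained: best (50 + 5)/170 − 25/170 = 17.6 points; worst 50/170 − (25 + 5)/170 = 11.8 points, p = 0.011.
- Nine erased per arm, 48/161 vs 24/161 retained: best (48 + 9)/170 − 24/170 = 19.4 points; worst 48/170 − (24 + 9)/170 = 8.8 points, p = 0.056.

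The p values are from the chi-square test without continuity correction.

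**The case against.** **Withdrawals may be few and even-handed.** This largely stands. The documents give neither a withdrawal rate nor a reason to expect withdrawal to differ by arm. The unblinding statement covers staff, not the parents who would withdraw. Outcome-related withdrawal that is equal in the two arms moves the difference by only 0.3 points at 5%. The large figures need 5% of one arm to leave, all of them failures.

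**Erasure may not be the sponsor's free choice.** This also stands in part. The protocol has ethics approval and the consent pages are not available here, so families may have been promised erasure. That limits the remedy for those families. It does not reconcile the two sections, and it does not prevent a tally by arm that holds no outcome data.

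**Three stronger readings are tempting, and the documents do not support them.**
- A reader might infer that the bias could never be bounded. That assumes the allocation record is destroyed too. The protocol does not say so, and if the record survives, numbers randomised minus numbers analysed can be recovered by arm.
- A reader might infer that interim results could not be reproduced, because the protocol plans that "Formal interim analyses of efficacy will be carried out by the DMB when 25%, 50% and 75% of the outcome data were available" and an outcome counted then could be erased later. That assumes the board's own copy is destroyed, which is not stated either.
- A reader might argue that a single erased infant could reverse the conclusion. Without continuity correction, 51/170 vs 36/170 gives p = 0.062, and erasing one NHFOV failure gives 0.049. But any result chosen at the threshold is this fragile, and with the correction this pair does not cross (0.082 to 0.066).

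**Conclusion.** The contradiction is real and lies in a stated rule, not in mere silence: destroying records on withdrawal cannot coexist with analysing every randomised infant, and no other section resolves it. It should be corrected.

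The size of the harm is conditional. The documents support saying that the primary risk difference could be biased, not that it will be. Losses balanced between arms cost little even at 5%. One-sided, outcome-related loss is small at 1-2% and becomes material at around 5%: power falls from 91.5% to 85.5%, or the difference is inflated from 15.0 to 16.0 points, with 5.9% false positives. The failures-only figures (72%, 19.5 points, 11.5%) mark the extreme and are not a forecast.

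These results rest on assumed withdrawal rates, the planned 30% and 15% failure rates, 170 infants per arm and a two-sided test.

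**What to change.** - Amend End of the study so that withdrawal stops further collection, while data already collected are kept and analysed, unless the parents ask for erasure or the consent given or local rules require it.
- In every case, retain the allocation record and a count of withdrawals and of erasures by arm, with no outcome data attached.
- Add to Statistical methods that, if any record is erased, best- and worst-case bounds for the primary risk difference will be reported on all randomised infants, and the analysis will not be described as full intention-to-treat.

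The first change needs a protocol amendment and new consent wording. If erasure has already been promised, it can apply only to families who consent afterwards. The count and the bounds cost almost nothing and need not wait for the consent change.

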### **Data collection**

All data for trial analysis are routine clinical items that can be obtained from the clinical notes. Data will be recorded in real time (every day) on web-based case report

forms provided by OpenCDMS. The website will be tested with fictitious data before the actual enrollment

Before the intervention begins: information on eligibility; baseline clinical informations, Silverman score, Critical risk index for babies-II score.

Following study intervention: ventilator parameters, SpO2, blood gas values (PaO2, PaCO2, SpO2 and pH) before intervention and intubation.

Follow-up: failed on assigned NIV at 72 hours or 7days, surfactant treatment, duration of the study intervention (NCPAP or NHFOV), airleaks, PDA, BPD, ROP >2nd stage, NEC ≥2nd stage, IVH >2nd grade, in-hospital mortality, composite mortality/BPD, weekly weight gain (in grams/day), duration of hospitalisation, thick secretions causing an airway obstruction, nasal trauma. fictitious data before the actual enrolment.

### **Sample size calculation**

According to the results of our last multicentre study, the risk of failure while receiving NCPAP for very preterm infants with RDS was 30%, and a reduction of 20% for babies receiving NHFOV. We decide to aim a difference of 15% in the rate of the respiratory support failure. Considering an alpha error of 0.05 and a power of 90%, 170 neonates would be needed in each group.

### **Statistical methods**

Outcomes will be analysed on an intention-to-treat basis. We will calculate a risk difference (with 95%CI) for dichotomous outcomes and mean (with 95%CI) or median (25–75th percentile, using Hodges-Lehmann) differences for continuous outcomes between the study groups. Continuous variables will be compared using

Student's t test or the Mann-Whitney rank sum test as appropriate. Categorical variables were compared using the  $\chi^2$  test. P values  $< 0.05$  were considered statistically significant.

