### **Exclusion criteria**

- i. Intubated for any reasons at birth
- ii. major congenital malformations or known complex congenital heart disease
- iii. transferred out of the NICU before randomisation

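### The primary analysis is unadjusted although gestational age is known for every infant before randomisation; a pre-specified GA-adjusted risk difference would add modest precision

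*Combined protocol and SAP*

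**What the plan says.** Under Statistical methods, the plan for binary outcomes is "We will calculate a risk difference (with 95%CI) for dichotomous outcomes". For the test it adds "Categorical variables were compared using the" χ² test. No section names a covariate, a stratified analysis or a regression model.

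Under Randomization, "Simple randomisation will be done according to a computer-generated random number table", so allocation is not stratified by GA. Infants enter "when patients fulfil all inclusion criteria". The Inclusion criteria list GA from 24+0 to 28+6 weeks, so GA must be known by then. Data collection confirms that eligibility is recorded first: "Before the intervention begins: information on eligibility; baseline clinical informations".

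The same Randomization section also says "Twins will all be allocated in the same treatment group", which matters for the standard error whichever estimate is used.

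**The concern.** GA is complete, is fixed before allocation, and spans five completed weeks. If less mature infants fail more often, part of the random variation in the unadjusted risk difference is due to GA, and data already in hand can remove it. Neither the design nor the analysis does so. The stake is efficiency: a wider confidence interval and slightly lower power than the same 340 infants could give. Bias and validity are not at issue.

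Simple randomisation also allows a chance imbalance in GA between the arms. A pre-specified adjustment deals with that without a model chosen after the data are seen.

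**Working it through.** **Inputs from Sample size calculation:** failure 30% on NCPAP, a target difference of 15 points (so 15% on NHFOV), alpha 0.05 (two-sided assumed), power 90%, 170 per group.

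**Inputs assumed, because the documents do not give them:** the odds ratio (OR) for failure per week of lower GA, and the distribution of GA.

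**1. The plan's own sample size.** The mean risk is (0.30 + 0.15)/2 = 0.225.

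n = [1.96·√(2·0.225·0.775) + 1.2816·√(0.30·0.70 + 0.15·0.85)]² / 0.15² = (1.157 + 0.745)² / 0.0225 ≈ 161 per arm.

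With the continuity correction, n = (161/4)·[1 + √(1 + 4/(161·0.15))]² ≈ 174. The stated 170 lies between the two and within 3% of 174.

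**2. Unadjusted analysis at 170 per arm.**
- χ² power: Φ[(0.15·√170 − 1.157)/0.581] = Φ(1.374) = 91.5%.
- SE = √[(0.21 + 0.1275)/170] = 0.0446, so the 95% CI half-width is 1.96 × 0.0446 = 8.7 points.
- Wald power: Φ(0.15/0.0446 − 1.96) = 92.0%.

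**3. Adjusted analysis, large-sample formula.** Let p0 and p1 be the GA-specific risks in the two arms, with overall risks held at 30% and 15%. The variance per infant of the standardised risk difference is

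V = 2·E[p0(1−p0) + p1(1−p1)] + Var(p1 − p0).

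The unadjusted value is 2·(0.21 + 0.1275) = 0.675.

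Example: OR 1.5, equal numbers in weeks 24 to 28. The logistic risks are p0 = 0.475, 0.376, 0.287, 0.211, 0.151 and p1 = 0.262, 0.191, 0.136, 0.095, 0.065. Then V = 2·(0.1967 + 0.1226) + 0.0021 = 0.641, and 0.641/0.675 = 0.949. The SE is √(0.641/340) = 0.0434, the half-width 8.5 points and Wald power 93.3%. This equals an unadjusted trial of 170/0.949 ≈ 179 per arm.

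**4. Simulation** (n = 340, no twins, simple 1:1 allocation, logistic model with arm and GA, 40,000 replicates). GA uniform over 24 to 28.9 weeks:

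| OR per week younger | Variance change | Unadjusted Wald power | Adjusted Wald power | Paired gain (points) |
|---|---|---|---|---|
| 1.0 | +0.3% | 92.0% | 91.9% | 0.0 |
| 1.15 | −0.4% | 91.9% | 92.1% | 0.2 |
| 1.3 | −1.9% | 91.9% | 92.5% | 0.5 |
| 1.5 | −4.9% | 91.8% | 93.2% | 1.4 |
| 1.8 | −10.1% | 91.8% | 94.3% | 2.5 |
| 2.0 | −13.6% | 91.7% | 94.9% | 3.2 |

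The half-width falls from 8.7 to 8.6, 8.5, 8.3 and 8.1 points at OR 1.3, 1.5, 1.8 and 2.0. With few infants under 26 weeks, OR 1.15, 1.3, 1.5 and 2.0 give variance changes of 0.0, −0.9, −2.5 and −7.9%, and gains of 0.1, 0.2, 0.9 and 2.1 points.

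**5. Type I error of the adjusted test** (30% in both arms, nominal 5%).
- n = 85, the 25% look: 6.0–6.1% with the uncorrected SE; 4.8% with a leverage-corrected SE and a t reference; 5.1% for χ².
- n = 340, no twins: 5.0–5.2% uncorrected, 4.7–4.9% corrected.
- n = 340, 25% of infants in twin pairs with latent correlation 0.3 (both assumed), SE clustered on mother: across two sets of runs, 4.8–5.5% uncorrected and 4.6–5.2% corrected. The planned χ², which ignores twins, gave 5.3–5.7% in one of these sets.

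The adjusted test is therefore sound at the final analysis, but the uncorrected version is too liberal at the early looks.

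**The case against.** The plan contains no error here. An unadjusted risk difference under intention to treat is coherent, transparent and adequately powered, so adjustment is optional. The benefit is also assumed: the documents give neither an association nor a GA distribution, and an even spread of GA is a favourable case. The Exclusion criteria remove infants "Intubated for any reasons at birth", which probably thins out the youngest. Failure can also rest on "attending physician determined that urgent intubation is necessary", which may weaken the link with GA. At OR 1.3 to 1.5 the interval narrows by only 0.1 to 0.2 points even with GA evenly spread, which would rarely change a conclusion. With the leverage correction, power is 91.6, 91.8 and 92.1% at OR 1.0, 1.15 and 1.3, so the gain over the unadjusted Wald test (91.9–92.0%) disappears when the association is weak.

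All of this stands as a limit on weight. It does not remove the point. Against the planned χ² (91.5–91.8%), the corrected adjusted test is about equal at worst and better from OR 1.3 upwards, and the loss if GA is irrelevant is negligible. Two neighbouring issues, twin clustering and the absence of interim thresholds, affect the unadjusted analysis equally and lend this point no weight. The 91.5% itself is for an uncorrected χ²; a continuity-corrected test, which the plan neither specifies nor excludes, would have 89.6% by exact calculation.

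**Conclusion.** The point holds as a recommended efficiency improvement. The planned analysis is valid and 170 per arm meets the stated power for an uncorrected χ² test, before twins and interim looks are considered. Pre-specified GA adjustment would reduce the variance by about 2% to 14% with evenly spread GA, or 1% to 8% with few infants under 26 weeks, for assumed odds ratios of 1.3 to 2.0 per week. The power gain is 0.5 to 3.2 points or 0.2 to 2.1 points respectively. It falls to 0.1 to 0.2 points at OR 1.15 and to nothing at 1.0, where 0.2% to 0.4% of variance is lost. These figures assume 30% versus 15%, 340 infants and no twins. Confidence in the size is medium, because the strength of the GA association cannot be read from the documents.

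**What to change.** Before unblinded results are seen, amend Statistical methods as follows.

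- **Final primary estimate:** the marginal risk difference standardised from a logistic model with arm and continuous GA, with a robust SE clustered on mother. The estimand stays a risk difference. The unadjusted risk difference and χ² test become supportive.
- **Interim looks at 25%, 50% and 75%:** do not use the uncorrected adjusted Wald test. Either (a) keep a χ²-type test, or (b) use the adjusted estimate with a leverage-corrected (HC3-type) SE clustered on mother and a t reference on n − 3 degrees of freedom. Under (b), check type I error at the thresholds the monitoring board adopts, since the Data monitoring board section gives none.
- **Other covariates:** the Critical risk index for babies-II score may be added only if fixed in advance. The figures here cover GA alone.

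**Cost:** SAP text and the final analysis program change, and a mother or twin-pair identifier must be kept in the data set. No new outcome or covariate data and no change to randomisation or sample size are needed. Option (a) needs no GA model at the interims. Option (b) needs the corrected SE programmed and checked; if also used at the final analysis, it costs about 0.3 points of power against the uncorrected version.

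### The P<0.05 rule is not limited to the primary outcome: with 14 secondary outcomes and no true effect on any, the chance of at least one false significant result is roughly 30% to 50%

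*Combined protocol and SAP*

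**What the plan says.** In the combined protocol and SAP, the Statistical methods section opens with "Outcomes will be analysed on an intention-to-treat basis". It then sets out risk differences for dichotomous outcomes and mean or median differences for continuous ones. Continuous variables are compared by "Student's t test or the Mann-Whitney rank sum test as appropriate", and categorical variables by the chi-square test. The section ends by stating that P values below 0.05 "were considered statistically significant".

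The Secondary outcomes section is numbered from 1 to 14, ending with "14) Rate of nasal trauma". Two entries matter for the calculation. Item "8) Composite mortality/BPD" is built from two other items on the list, BPD (item 2) and in-hospital death (item 7). Item "9) Weekly weight gain (in grams/day) for the first 4 weeks of life or until NICU discharge, whichever comes first" is measured repeatedly.

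The Sample size calculation refers only to respiratory support failure: "Considering an alpha error of 0.05 and a power of 90"%, giving 170 per group.

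**The concern.** The closing rule cannot be read as applying to the primary outcome alone. The primary outcome, need for invasive ventilation within 72 hours, is dichotomous, yet the same section gives methods for continuous outcomes. The only continuous outcomes in the plan are secondary: weight gain, time on non-invasive support and length of stay (items 9 to 11). So the rule reaches the secondary list, and no section limits it, ranks the outcomes or allows for their number.

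The list includes death, BPD, their composite, severe IVH, NEC and air leaks. As written, the plan permits a chance result on any of these to be called a statistically significant benefit or harm of NHFOV, even if the primary outcome shows no difference. A later decision not to stress such a result, or to stress it, would have no pre-specified basis.

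**Working it through.** **1. The plan's own figure.** Inputs from the Sample size calculation: 30% failure on NCPAP, a target difference of 15 percentage points (read as 30% against 15%), alpha 0.05, power 90%. With mean proportion 0.225, the two-sided pooled formula is

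n = [1.960 × √(2 × 0.225 × 0.775) + 1.282 × √(0.30 × 0.70 + 0.15 × 0.85)]² / 0.15² ≈ 161 per group,

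or 174 with a continuity correction. The stated 170 lies between these and is within 3% of the second; it gives 91.5% power without the correction. One-sided versions give 131 and 144. The plan does not state sidedness, but 170 fits a two-sided 0.05 for the primary outcome. The document gives no error rate for the secondary outcomes, so there is no figure to reproduce there.

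**2. Independent tests, no true effects.** For k tests at 0.05, the chance of at least one P<0.05 is 1 − 0.95^k.

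- k = 14: 1 − 0.95^14 = 51.2%. Expected false positives: 14 × 0.05 = 0.70.
- k = 17, if weight gain were tested in each of four weeks (14 − 1 + 4): 1 − 0.95^17 = 58.2%. Expected false positives: 17 × 0.05 = 0.85.
- If three of the 14 effects were real, the 11 remaining nulls give 1 − 0.95^11 = 43.1%.

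**3. Correlated tests.** The outcomes are dependent, and the document gives no correlations. The table assumes equally correlated normal test statistics and two-sided 0.05. Rows 0.1 to 0.7 are simulated, with at least 200,000 draws per entry.

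| Assumed common correlation | 14 tests | 17 tests |
|---|---|---|
| 0 | 51.2% | 58.2% |
| 0.1 | 50.2% | 56.9% |
| 0.2 | 47.5% | 53.7% |
| 0.3 | 43.8% | 49.4% |
| 0.4 | 39.5% | 44.1% |
| 0.5 | 34.8% | 38.6% |
| 0.6 | 29.9% | 32.8% |
| 0.7 | 24.9% | 27.2% |

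**4. A null trial built like this one.** Trials of 170 per arm were simulated with the composite formed from death and BPD, and with correlated weekly weights. Event rates were assumed, because the document gives none: two sets, spanning 1% to 60%. Patient-level correlation was set from 0 to 0.5. With the chi-square test uncorrected, 14 tests gave 41% to 50% and 17 gave 43% to 55%. With a Yates correction, which the plan does not mention, they gave about 30% to 39% and 33% to 46%.

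**The case against.** The strongest reply is that the plan is conventional. It names one primary outcome, bases alpha and power on that outcome alone, labels the rest secondary and leads with estimates and 95% confidence intervals. On this view the last sentence is a generic convention, and readers know how to treat secondary P values. Part of this stands: the sentence permits significance claims but does not show that they will be made. The label alone, however, does not take the secondary outcomes out of the rule.

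A reader might also infer more than the document supports:

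- **That a false finding is as likely as not.** This needs both no true secondary effect and near-independence. The composite contains two other listed outcomes, so 51% is close to an upper value for 14 tests.
- **That there are 17 tests.** The document says how weight gain is measured, not that each week is tested.
- **That this is the chance of a false claim on a practice-changing outcome.** For the six outcomes named above, independence gives 1 − 0.95^6 = 26%, or 1 − 0.975^6 = 14% for a false benefit only. Overlap within the composite lowers both.
- **That the primary result is compromised.** The number of secondary outcomes does not alter the primary significance level or the 170 per group. The planned interim looks are a separate matter.

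One technical reservation also stands. The expected counts of 0.70 and 0.85 do not depend on correlation only if every test has exactly 5% size. At 170 per arm the uncorrected chi-square has size about 3.5% at an assumed 1% event rate and 4.5% at 2%.

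**Conclusion.** The concern holds within stated limits. One unqualified P<0.05 rule covers all 14 secondary outcomes. If NHFOV affects none of them, the chance of at least one false significant result at the final analysis is roughly 30% to 50%: 51% under independence, 30% at an assumed common correlation of 0.6, and lower still if correlation is stronger. Even 30% is six times the nominal 5%. The figure would be somewhat higher if weight gain were tested week by week. It rests on assumed correlations and, for the simulated trial, on assumed event rates.

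This should be corrected because the remedy costs little, but it bears only on claims about secondary outcomes.

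**What to change.** Replace the last sentence of the Statistical methods section with:

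*The primary outcome will be tested at a two-sided significance level of 0.05. Secondary outcomes, including harms, will be reported as differences with 95% CIs not adjusted for multiplicity, without claims of statistical significance, and interpreted as supportive or exploratory; harm signals will be reported and considered regardless of P value.*

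This keeps the planned estimates and intervals, adds no patients and makes the sidedness of the primary test explicit. The cost is that no secondary result can be called statistically significant, however small its P value. The change governs claims, not chance: an unadjusted interval may still exclude zero by chance about as often as before, which is why the text says that the intervals are unadjusted.

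A formal adjustment such as Holm's procedure over the 14 outcomes (first threshold 0.05/14 = 0.0036) is not recommended here. Unless made conditional on the primary result, it would still allow secondary claims when that result is negative. It would also make real harms, such as air leaks or nasal trauma, harder to declare.
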